2.20 EVALUATION OF SAFETY

All enrolled subjects who have received SOF/VEL/VOX FDC will be evaluated for safety. Safety will be assessed by physical examination, vital signs, hematology, and chemistries. The severity of signs, symptoms, and AEs will be determined by using the 2004 DAIDS Toxicity Severity Scale.

2.20.1 Follow-up of Abnormal Laboratory Test Values

In the event of unexplained abnormal laboratory test values, the tests should be repeated immediately and followed up until they have returned to the normal range and/or an adequate explanation of the abnormality is found. If a clear explanation is established it should be recorded.

2.20.2 Criteria for Premature Withdrawal and Stopping Rules

Subjects have the right to withdraw from the study at any time for any reason. Subjects who withdraw early or who are terminated from study by the Investigator will not be replaced unless they have received no study drugs. In addition to the criteria for stopping subject treatment described in Dose Modification and Treatment Failure Sections, the Investigator or designee also has the right to withdraw subjects from the study for any of the following:

- 1. Development of life-threatening infection (requiring withdrawal of study drugs for more than 6 weeks) or malignancy.
- 2. Participant's desire to leave study.
- 3. Pregnancy or breastfeeding.
- 4. Participant's non-compliance. If a subject misses 5 or more total study visits or > 3 weeks of study drug, the subject will be removed from the protocol at the discretion of the Investigator or designee.
- 5. Termination of study.
- 6. Development of liver decompensation with elevated Child-Turcotte-Pugh score of 8 or more.
- 7. If SOF/VEL/VOX FDC is permanently discontinued by the pharmaceutical company.
- 8. Development of a medical condition, such as hepatocellular carcinoma, that in the opinion of the Investigator, it is in the subject's best interest to discontinue study drug even if criteria requiring drug discontinuation have not been met.
- 9. Request of the primary care provider or Investigator if s/he thinks the study is no longer in the best interest of the subject.
- 10. Clinical reasons believed life threatening by the physician.
- 11. If the subject is judged by the Investigator to be at significant risk.
- 12. Subjects may decide at any point not to have their samples stored. This will be treated as a withdrawal of the consent and in this case, the Principal Investigator will assure the destruction of all known remaining samples and report what was done to both the subject and to the IRB. This decision will affect the subject's participation in this protocol but may not affect participations in any other protocols at UMD.

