2.19 FAILURES, EARLY TERMINATION AND EARLY TREATMENT DISCONTINUATION

Participants who prematurely discontinue study agents due to toxicity will be followed closely for resolution of symptoms, until final outcome is known or until the end of the study follow-up period.

Participants requiring discontinuation, as well as those who elect to discontinue study drugs prior to treatment completion for medical or personal reasons, will continue to follow the general study schedule of assessments unless unwilling to do so, in which case they may be seen at least every 12 weeks for safety and research labs until the end of the study. The participant should have an end of treatment visit scheduled as soon as possible after all therapy is discontinued if willing. Any subject continuing in the study will be followed closely for resolution of active laboratory abnormalities or adverse events that are considered related to the study agents. Participants with undetectable HCV RNA at the end of treatment should continue to follow the scheduled SVR4, SVR12, and SVR24 visits following the date of their last dose of therapy while remaining undetectable.

Participants who have detectable HCV RNA at the end of treatment or who relapse posttreatment will be asked to return for additional visits at least every 12 weeks after the end of treatment for up to a total of 24 weeks or on a separate natural history protocol to determine the persistence of any HCV populations with treatment-emergent substitutions conferring resistance to SOF or GS-5885 or VOX. Any subject continuing in the study will be followed closely for resolution of active laboratory abnormalities or adverse events that are considered related to the study agents.

Samples collected will be used to determine the durability of response or the dynamics of any changes in resistance conferring mutations. The reason for any early termination should be documented.

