3.4.1 Dose Modification for SOF/VEL/VOX

Dose modifications will not be permitted. If a subject forgets to take the medication at the correct time, it may be taken later in the day; however, no more than a single dose should be taken on any calendar day. The subject should resume the standing dosing schedule on the next day. Any treatment interruption or discontinuation will be recorded including the reason for the interruption or discontinuation.

3.4.2 Treatment Failure / Drug Discontinuation

See also Criteria for premature withdrawal of subjects (2.20.2). Subjects will be considered treatment failures and will discontinue SOF/VEL/VOX FDC if they meet any of the following criteria while taking study drugs:

- HCV RNA greater than LLOQ after 2 prior consecutive HCV RNA values less than the LLOQ
- Greater than a 1 log₁₀ increase in HCV RNA from nadir
- Less than a 2 log₁₀ decline in HCV RNA after 4 weeks of treatment (unless >2 log drop would be below LLOQ)
- HCV RNA \geq LLOQ after 8 weeks of treatment

If any of these should occur in a patient who is currently on study drugs, the subject should return within one week for a confirmatory test. If the confirmatory test also meets the same criteria, the subject will be considered a treatment failure and should be discontinued from therapy. The anticipated clinical impact of discontinuation should be discussed in advance with the Medical Monitor (MM) if possible, particularly if discontinuation is thought to pose a risk to the overall clinical wellbeing of the subject. Those who are discontinued will continue to follow the general study schedule of assessments unless unwilling to do so, in which case they may be seen at least every 12 weeks for safety and research labs until the end of the study. Subjects will be followed closely for resolution of active laboratory abnormalities or adverse events which are considered related to the study agents prior to starting the revised schedule.

Subjects who meet any of the following laboratory criteria must stop all study medication(s):

- Elevation of ALT >5x OR AST >5x Day 0, confirmed by immediate repeat testing
- Abnormal elevation of ALT >3 x Day 0 *and* total bilirubin >2 x ULN, confirmed by immediate repeat testing
- Elevation of ALT >15 x ULN confirmed by immediate repeat testing
- Any Grade 3 or greater rash associated with constitutional symptoms
- Any Grade 4 event assessed as related to treatment with SOF/VEL/VOX FDC
- Pregnancy

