4.1 SAMPLE SIZE

We anticipate enrolling approximately 60 patients with cirrhosis and 60 patients without cirrhosis, for a total of 120 HCV, genotype 1, infected subjects who have previously been treated with unsuccessful combination DAA-based therapy.

An anticipated sample size of approximately 120 patients will provide a 97% power to detect at least an absolute 15% improvement in SVR_{12} from the conservative estimate of 70%²⁰ by using a 2-sided, exact, 1-sample binomial test at a significant level of 0.05 (See Table 4-1).

H _o SVR12	H _a SVR12	Sample Size	Power
70%	80%	120	0.641
70%	85%	120	0.968
70%	90%	120	>0.999
70%	95%	120	>0.999

In terms of safety, a sample size of 120 is sufficient to have high probability of observing at least 1 adverse event of probability 5% or more. If the true event probability is 5% or more, there is about a 99.8% chance of observing at least 1 such adverse event. Consequently, if no one has a given type of AE, we can be confident that its true probability is under 5%. This trial will provide preliminary evidence on the safety and efficacy of SOF/VEL/VOX. A previous study of SOF/VEL FDC in subjects with genotype 1 led to a sustained virologic response at Week 12 (SVR₁₂) in all participants. We therefore expect SVR to 80% or higher. If the true suppression rate is 80%, we will be able to estimate the probability of suppression to within approximately $\pm 1.96[(.8)(1-.8)/120]^{1/2}=.07$ (Table 4-2). For sample sizes shown in row 1, row 2 gives the accuracies of the estimates of the proportion of patients suppressed to below the limit of detection (based on a 95% confidence interval).

Table 4-2: Sample Size

n=50	n=75	n=100	n=120
±.11	±.09	$\pm.08$	±.07

AE probabilities are shown in Table 4-3, wherein for a given N, the probability of observing at least 1 participant with the AE among study participants. We selected at least 100 participants based on the ability to detect adverse event rates of a frequency of 1% and 5% with 63% and 99% probability, respectively.

Table 4-3: Adverse Event Probability Table

	Probability of Adverse Event				
	0.01	0.05	0.10	0.15	
N=75	52%	98%	>99.9%	>99.9%	
N=100	63%	99%	>99.9%	>99.9%	
N=120	70%	99.8	>99.9%	>99.9%	

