4.2 DATA HANDLING CONVENTIONS

Missing data can have an impact upon the interpretation of the trial data. Other than the endpoints discussed below, values for missing data will not be imputed.

For the analysis of post-baseline categorical efficacy endpoints, if a data point is missing and is preceded and followed in time by values that are deemed successes, then the missing data point will be termed a success; otherwise the data point will be termed a failure.

Any subject with missing data due to premature discontinuation of the study medication will be considered a failure at the time points on, or following, the date of discontinuation. If no HCV RNA values are obtained after the last dose of study medication, the subject will be considered a treatment failure for the SVR endpoints.

Where appropriate, safety data for subjects that did not complete the study will be included in summary statistics. For example,

- If a subject received study medication, the subject will be included in a summary of adverse events according to the treatment received; otherwise, if the subject is not dosed then they will be excluded from the summary.
- If safety laboratory results for a subject are missing for any reason at a time point, the subject will be excluded from the calculation of summary statistics for that time point. If the subject is missing a pre-dose value, then the subject will be excluded from the calculation of summary statistics for the pre-dose value and the change from pre-dose values.

Values for missing vital signs data will not be imputed; however, a missing Day 0 result will be replaced with a screening result, if available.

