4.4 ADVERSE EVENTS

Events will be summarized on the basis of the date of onset for the event. A treatment-emergent adverse event will be defined as any new or worsening adverse event that begins on or after the date of first dose of study drug up to the date of last dose of study drug plus 30 days.

Summaries (number and percentage of subjects) of treatment-emergent adverse events will be provided.

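### Section 2.20.2 lets the investigator withdraw subjects from the study on grounds for stopping drug, although 2.19 keeps subjects who stop drug in follow-up; SVR12 can be biased downward and safety follow-up cut short

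*Combined protocol and SAP*

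**What the plan says.** Protocol section 2.20.2 gives grounds for taking a subject out of the study: "the Investigator or designee also has the right to withdraw subjects from the study for any of the following". Item 3 is pregnancy or breastfeeding. Item 4 covers five or more missed visits, or more than three weeks of missed drug, after which "the subject will be removed from the protocol at the discretion of the Investigator or designee". Item 8 covers a new medical condition for which the investigator judges that "it is in the subject's best interest to discontinue study drug even if criteria requiring drug discontinuation have not been met". The section adds that dosed subjects who leave are not replaced.

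Section 2.19 deals with subjects who have to stop drug and with those who choose to stop for medical or personal reasons. They "will continue to follow the general study schedule of assessments unless unwilling to do so"; in that case they may still be seen at least every 12 weeks. Section 3.4.2 has a similar sentence, "Those who are discontinued will continue to follow the general study schedule of assessments unless unwilling to do so", in its paragraph on confirmed virologic failure. Pregnancy appears in a separate list in 3.4.2 of events that require all study medication to stop.

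Under section 4.1.1 the primary analysis includes every enrolled subject who took at least one dose. Section 4.2 counts a missing categorical efficacy value as a failure unless there are successes both before and after it, and counts missing data after premature discontinuation as failure. With regard to SVR it adds: "If no HCV RNA values are obtained after the last dose of study medication, the subject will be considered a treatment failure". Section 4.4 defines treatment-emergent events as those beginning from first dose "up to the date of last dose of study drug plus 30 days", and section 8.7 collects adverse events to the end of study follow-up.

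**The concern.** Stopping drug and leaving the study are different events with different consequences for the data, and 2.20.2 runs them together. Item 8 even speaks of stopping drug while sitting in a list of reasons for study withdrawal. A subject who stops drug for such a reason can be kept to post-treatment week 12 under 2.19 or withdrawn under 2.20.2. The choice lies with an investigator who knows the treatment and the on-treatment HCV RNA.

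The choice can decide the primary efficacy outcome. A retained subject with HCV RNA below LLOQ 12 weeks after the last dose is a responder; the same subject, if removed, is normally a failure. On safety, subjects withdrawn for a serious medical condition are among the most informative, and their planned follow-up may be shortened. The Study Summary makes the incidence of grade 3 and 4 adverse events a primary endpoint.

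**Working it through.** **1. The rules side by side**

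| Ground | Section 2.20.2 | Elsewhere |
|---|---|---|
| Pregnancy (item 3) | may be withdrawn from the study | 3.4.2: drug must stop; 2.19: subjects who must stop drug stay on schedule if willing |
| Over 3 weeks of drug missed (part of item 4) | removal from the protocol, at discretion | 2.19, if dosing has been stopped: stay on schedule if willing |
| New condition making it best to stop drug (item 8) | may be withdrawn from the study | 2.19: stay on schedule if willing |

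Section 3.4.2 refers the reader to 2.20.2, but no section says which rule prevails.

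**2. How a removed subject is scored**

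The subject stays in the denominator (4.1.1) and is not replaced (2.20.2). If there is no HCV RNA after the last dose, 4.2 scores failure directly. If an end-of-treatment sample was taken, the general rule in 4.2 applies: SVR12 is missing, no later success follows it, so it is a failure. If the subject is kept, the observed week-12 value counts. Response after short exposure is possible on the protocol's own evidence: section 1.6.2 reports SVR12 in 20/30 (67%) of subjects who had failed two DAAs and then had 6 weeks of SOF/VEL+VOX.

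**3. The plan's own power figure**

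Inputs from section 4.1: n = 120, null rate 70%, two-sided exact binomial test, alpha 0.05. With at most 0.025 in each tail, the test rejects upward at 95 or more responders (tail 0.0159) and downward at 73 or fewer (tail 0.0200). Power is 0.641 at 80%, 0.968 at 85%, and above 0.999 at 90% and 95%. All four rows of Table 4-1 are reproduced.

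**4. Size per subject**

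Each removed subject who would have responded lowers observed SVR12 by 1/120 = 0.83 points.

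**5. Illustration with an assumed removal share**

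No removal rate is given. Suppose a share d is removed, all are scored as failures, and they would otherwise have responded at the common rate p. The observed rate is then p(1 - d), tested against the same limit of 95/120.

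| True p | Assumed d | Observed rate | Power |
|---|---|---|---|
| 85% | 0 | 85% | 0.968 |
| 85% | 2% | 0.85 x 0.98 = 83.3% | 0.906 |
| 85% | 5% | 0.85 x 0.95 = 80.75% | 0.716 |
| 85% | 10% | 0.85 x 0.90 = 76.5% | 0.285 |
| 95% | 5% | 0.95 x 0.95 = 90.25% | >0.999 |
| 95% | 10% | 0.95 x 0.90 = 85.5% | 0.978 |

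**6. Safety window**

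If observation ended on the day of the last dose, 30 days of the treatment-emergent window would be lost. For a stop at week 4 that is 30/(28 + 30) = 30/58 = 52% of the window; for a stop at week 12 it is 30/(84 + 30) = 30/114 = 26%. Both figures assume no further contact, which the documents do not state.

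**The case against.** The strongest reply is that 2.20.2 is a discretionary power alongside a default in 2.19, and that its opening already distinguishes stopping treatment from study withdrawal. A reader might infer that 2.20.2 requires these subjects to be removed. It does not: it gives a right, and item 4 is at discretion. That point stands, but the discretion is what leaves the primary outcome open to choice.

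A reader might also infer that 3.4.2 itself keeps pregnant subjects in follow-up. It does not: its follow-up sentence belongs to the virologic failure paragraph, and the list that includes pregnancy has no such sentence. The contrast rests on 2.19, which covers anyone who has to stop drug.

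Nor do the documents show that a removed subject has no HCV RNA after the last dose. Section 2.17 allows the week 12 assessments at any end-of-treatment visit, and 2.19 asks for such a visit soon after therapy ends. This changes which rule in 4.2 applies, but normally not the result. Scoring missing as failure is a deliberate conservative convention and is not at fault. Under item 4, a subject who has missed five of ten visits may lack SVR12 data whether removed or not, and confirmed virologic failures under 3.4.2 are failures either way.

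On safety, some information survives. The triggering event is recorded, and it suffices for the safety endpoint in 4.1.3 (adverse events leading to permanent discontinuation). Pregnancy outcomes are reported to the medical monitor and the clinical safety office, and section 8.8 covers related serious events reported after follow-up. Section 8.8 also follows events to outcome or the end of follow-up, but does not expressly extend this to removed subjects.

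**Conclusion.** The concern holds in this form: 2.20.2 permits, without requiring, study withdrawal on grounds that are in substance drug stops, and this conflicts with 2.19. The effect on SVR12 is downward, at 0.83 points for each removed subject who would have responded.

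A reader might infer a total loss such as 2.5 to 5.0 points (3/120 to 6/120). The documents do not support a total: they give no removal rate, and that range also takes every removed subject as a responder. A reader might also infer that the efficacy claim is in danger. The bias cannot help a false claim that SVR12 exceeds 70%. At a true 95%, the lower end of the 95-97% cited in section 1.6.4, power stays above 0.999 with an assumed 5% removed. Only near the 85% design alternative would the loss of power be material (0.968 to 0.716 at 5%). The practical losses are accuracy of the SVR12 estimate and completeness of follow-up for grade 3 and 4 events. The change is worth making, because it touches both primary endpoints and costs little.

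**What to change.** Reconcile 2.19 and 2.20.2 so that stopping study drug and leaving the study are separate decisions. Suggested rule for 2.20.2: a dosed subject whom the investigator withdraws on any listed ground remains in off-drug follow-up under 2.19 unless unwilling. The exceptions are the subject's own wish to leave, withdrawal of consent, and termination of the study. Follow-up should include adverse event collection to at least 30 days after the last dose, and HCV RNA at 12 and 24 weeks after the last dose. In item 4, reconcile removal from the protocol with this follow-up.

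The clinical triggers and the decision on when drug is stopped remain with the sponsor. The sponsor should also state for items 7, 9, 10 and 11 whether each ends dosing, participation or both, since their wording does not settle it.

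The cost is a wording change and a few extra follow-up visits, which 2.19 already provides for. The sample size and the missing-data rule in 4.2 need no change.

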3 STUDY AGENTS

3.1 DISPOSITION AND DISPENSATION

Study agents will be distributed via the IHV Pharmacy according to standard pharmacy procedures.

All drug products will be stored in a securely locked area, accessible only to authorized site personnel. To ensure the stability of the study drug and to ensure proper product identification, the drug product should not be stored in a container other than the container in which they are supplied. Consideration will be given to handling, preparation, and disposal through measures that minimize drug contact with the body. Appropriate precautions will be followed to avoid direct eye contact or exposure through inhalation when handling study drugs.

3.2 PACKAGING AND LABELING OF STUDY DRUGS

Each bottle will be individually labeled with the patient ID number, dosing instructions, recommended storage conditions, the name and address of the manufacturer, Investigational Use

Statement ("Caution: New Drug – Limited by Federal [USA] Law to Investigational Use") and that the agent should be kept out of reach of children.

3.2.1 Formulation

SOF/VEL/VOX fixed dose combination (FDC) tablets are beige, capsule-shaped, film-coated tablets containing 400 mg of sofosbuvir, 100 mg of VEL, and 100 mg of VOX. The tablets are debossed with "GSI" on one side and "3" on the other side. In addition to the active ingredients, the tablets contain the following inactive ingredients: copovidone, microcrystalline cellulose, lactose monohydrate, colloidal silicon dioxide, croscarmellose sodium and magnesium stearate. The tablet film-coating material also contains polyvinyl alcohol, titanium dioxide, macrogol/PEG 3350, talc, iron oxide yellow, iron oxide red, ferrosoferric oxide.

3.2.2 Packaging and Labeling

SOF/VEL/VOX FDC tablets are packaged in white, high density polyethylene (HDPE) bottles. Each bottle contains 28 tablets and a silica gel desiccant canister or sachet and polyester packing material. Each bottle is enclosed with a white, continuous thread, child-resistant screw cap with an induction-sealed, aluminum-faced liner.

Sufficient quantities of SOF/VEL/VOX FDC tablets to complete the entire study will be shipped from Gilead Sciences Materials & Logistics (or its designee).

3.2.3 Storage and Handling

SOF/VEL/VOX FDC bottles should be stored at controlled room temperature until required for administration. Controlled room temperature is defined as 25°C (77°F); excursions are permitted between 15°C and 30°C (59°F to 86°F).

All drug products will be stored in a securely locked area, accessible only to authorized site personnel. To ensure the stability of the study drug and to ensure proper product identification, the drug product will not be stored prior to dispensing in a container other than the container in which they are supplied. Consideration should be given to handling, preparation, and disposal through measures that minimize drug contact with the body. Appropriate precautions should be followed to avoid direct eye contact or exposure through inhalation when handling SOF/VEL/VOX FDC.

